## 7.1.1 Molecular pre-screening

### 7.1.1.1 Tumor sample requirement

The patient must sign the molecular pre-screening ICF before the tumor sample can be provided to a Novartis-designated central laboratory for molecular screening. A newly obtained tumor biopsy (preferred) or archival tumor tissue (block or slides) should be submitted to test cMET amplification and/or cMET mutation status. Archival tumor tissue obtained at the time of diagnosis of NSCLC or any time since is acceptable and may consist of a formalin fixed paraffin embedded (FFPE) tumor block tumor or slides; if more than one archival tissue sample (block or slides) is available, tissue from most recent archival sample is preferred. Samples obtained from bone metastases are not acceptable. Amplification and mutation status will be determined centrally at a Novartis designated laboratory.

Additionally, a portion of these samples will be retrospectively analyzed by NGS for targets including amplification and mutation of cMET.

[figure not shown]
If a tumor block or new biopsy is provided, the remaining tissue from pre-screen failure samples will be returned to the site. However, a small amount of any remaining tissue will be retained from all patients, under the control of Novartis, to support the development of future companion diagnostic test(s) with a method such as NGS. If patient is enrolled, the remaining block will be sent to Novartis-designated vendor. Only if the site requests the sample to be returned, approximately 3 slides will be cut prior to sending the remaining block back to the site. Additional tissue may be requested, retrospectively, if available, to support the development of future NGS companion diagnostics if the remaining tissue sample is insufficient for analysis.

If ALK testing is not available locally, confirmation of ALK-negative rearrangement status at a Novartis-designated central laboratory using a validated ALK testing is required to confirm patient's eligibility. In this case, the tumor sample provided, either as newly obtained tumor biopsy (preferred) or archival tumor tissue (block or slides preferably from the same tumor) will be used to determine cMET amplification and mutation status as well as ALK rearrangement status.

The cMET amplification, cMET mutation and ALK rearrangement status where analyzed will be communicated to the site within approximately 5 working days of receipt of the sample at the central laboratory. Results of the analysis must be received before any additional tests can be performed to determine the patient's eligibility for the study.

Instructions for tumor sampling, preparation and packing/shipping are described in a separate laboratory manual.

If a patient's cMET amplification and/or mutation status is known via a local result, confirmation of their status via a Novartis-designated central laboratory is required to confirm eligibility.

Please refer to [Section 6.5](#) for patient numbering, IRT procedures and cohort assignment.

### 7.1.2 Screening

Once the cMET amplification and mutation status (and ALK rearrangement status, if applicable) is confirmed by the central designated laboratory performing the molecular pre-screening analysis, patients may enter the screening phase. Written informed consent must be obtained before any study specific procedure is performed. Screening assessments to confirm eligibility into the main study should be performed as per the schedule of assessments between Day-28 and Day-1. Laboratory assessments performed as part of the screening evaluations will not require to be repeated prior to dosing if performed within 7 days prior to the first dose of study treatment. Only laboratory results from the Novartis-designated central Laboratory can be used to determine patient's eligibility for the study. The cardiac eligibility criteria should be assessed with the central ECG report.

A patient who has a laboratory test result(s) that does not satisfy the entrance criteria may have the test(s) repeated within the 28-day screening period. In these cases, the patient is not required to sign another ICF and must retain the same Subject No. In the event that the laboratory test(s) cannot be performed within the 28 days of the original screening visit, or the re-test(s) do not meet the entrance criteria, or other eligibility criteria have changed and are not met anymore, the patient is considered a screen failure, and must be discontinued from the study. A new ICF will need to be signed if the investigator chooses to re-screen the patient after a patient has screen failed, however, the Subject No will remain the same.

Patients who fail screening due to laboratory parameters (inclusion criterion # 7) or baseline tumor assessment (inclusion criterion # 5) may be re-screened. Patients who met all eligibility criteria but fail to be started on treatment as scheduled may be also re-screened, provided the patient was not registered previously in IRT as having entered the Treatment Period. Re-screening of a patient must be performed within the 28-day re-screening period, and is allowed only once per patient. All required screening activities must be performed when the patient is re-screened for participation in the study.

All eligibility criteria must be re-checked, based on the most recent data available, and met prior to enrollment of the patient into the study.

If any cohort/sub-cohort is closed to enrollment, then only patients with the cMET amplification or mutation status required for the open cohort(s)/sub-cohort(s) will be eligible for main screening for study enrollment. Enrollment of patients with GCN  $\geq 4$  and  $< 5$  in Cohort 2 may be stopped when the target of 60% (i.e. at least 17 patients for the IA and 41 patients for the final enrollment) with GCN  $\geq 4$  and  $< 5$  is reached.

#### 7.1.2.1 Eligibility screening

The main screening period commences as soon as the patient signs the main ICF and ends when the patient fails screening or starts treatment. Evaluations will be performed within 4 weeks (i.e., within 28 calendar days) prior to the first dose of study drug, unless otherwise noted. All screening assessments, including laboratory assessments, must be performed as described in the protocol ([Table 7-1](#)). Any imaging assessments already completed as

patient's standard of care within 28 days prior to start of treatment, including before signing the main study ICF, can be considered as the baseline images for this study. Any imaging assessments obtained after first dose cannot be considered baseline images.

### Eligibility Check

In order to determine and confirm the eligibility of the patient, once all screening procedures are completed, an eligibility checklist must be completed via IRT by the investigator or designee prior to receiving the first dose of study drug (Section 4.1.2). Please refer to and comply with the detailed guidelines in the IRT manual.

After the eligibility has been checked and confirmed that the patient is eligible for the trial, then the patient can be enrolled into the study.

Approximately 30 enrolled patients at selected sites (regardless of cohort assignment) will have full PK samples and ECGs collected. The rest of the patients will have sparse PK samples and ECGs collected (see Table 7-5, Table 7-6, Table 7-7 and Table 7-8). At the time of eligibility confirmation, the IRT system will inform the site which PK and ECG schedule should be followed by the patient.

Patients who fail to be started on treatment may be re-screened (see Section 7.1.2), provided the patient was not registered previously in IRT as having entered the Treatment Period. In this situation, the Subject No. which was previously assigned to the patient will be re-applied to the same patient throughout his/her entire study participation.

#### 7.1.2.2 Information to be collected on screening failures

Patients who signed an Informed Consent Form but failed to be started on treatment for any reason will be considered a screen failure. Both patients who signed a molecular pre-screening ICF but are considered ineligible after molecular pre-screening, as well as patients who are found not eligible after signing the main study consent will be considered as screening failures, and data will be handled in the same manner. The reason for not satisfying eligibility criteria and not being enrolled will be entered on the Screening Phase Disposition eCRF Page. The following eCRF pages must be completed for screening failure patients:

- EGFR molecular status
- ALK rearrangement status
- Information on local testing for cMET amplification and cMET mutation prior to patient consideration for this study, if available
- NSCLC diagnosis and extent of disease, including:
  - Date of diagnosis and stage of NSCLC
  - Site of active disease
  - Characteristics of disease
- Tumor samples collection for cMET and ALK (if local ALK status is not available)
- Screening Phase Disposition
- Demography

- Informed consent
- Inclusion/Exclusion Criteria
- Withdrawal of consent (if applicable)
- Death (if applicable)

No other data will be entered into the clinical database for patients who are screen failures, unless the patient experienced a Serious Adverse Event during the Screening Phase (see [Section 8](#) for SAE reporting details). For molecular pre-screening failures, only SAEs possibly related to a study procedure will be reported.

If the patient fails to be enrolled, the IRT must be notified within 2 days of the screen fail that the patient was not enrolled.

### **7.1.2.3 Patient demographics and other baseline characteristics**

Data to be collected include:

- EGFR molecular status
- ALK rearrangement status
- Information on local testing for cMET amplification and cMET mutation prior to patient consideration for this study, if available.
- Demography (including: date of birth, age, patient initials, gender, childbearing potential, race and ethnicity, or as allowed by local regulations)
- Relevant medical history
- Smoking history
- Cohort/sub-cohort assignment
- NSCLC diagnosis and extent of disease, including:
  - Date of diagnosis and stage of NSCLC
  - Site of active disease
  - Characteristics of disease
- Prior antineoplastic therapies (medications, radiation, surgeries)
- Prior and current concomitant medications, surgical and medical procedures

Note: All other medications taken within 28 days before the first dose of study treatment is administered must be recorded on the Prior and current concomitant medication eCRF page and updated on an ongoing basis if there is new change to the medication.

### **7.1.3 Treatment period**

Following completion of screening procedures and confirmation of patient eligibility, the patient will be enrolled via the IRT in one of the cohorts based on the cMET amplification status. At the time of eligibility confirmation, the IRT system will inform the site about which PK and ECG schedule should be followed by the patient.

The study treatment will begin on Cycle 1, Day 1 with the first administration of INC280 and does not have fixed treatment duration. Information on drug exposure will be collected on the Dosage Administration Record eCRF.

### 7.1.4 Discontinuation of study treatment

Patients may voluntarily discontinue from the study treatment for any reason at any time. If a patient decides to discontinue from the study treatment, the investigator should make a reasonable effort (e.g. telephone, e-mail, letter) to understand the primary reason for this decision and record this information in the patient's chart and on the appropriate CRF pages. They may be considered withdrawn if they state an intention to withdraw, fail to return for visits, or become lost to follow-up for any other reason.

The investigator should discontinue study treatment for a given patient if, on balance, he/she believes that continuation would be detrimental to the patient's well-being.

Study treatment must be discontinued under the following circumstances:

- Emergence of specific adverse events or laboratory abnormalities under some circumstances as outlined in [Section 6](#)
- Pregnancy (pregnancy will be followed for outcome)
- Use of prohibited treatments (refer to [Section 6.4.3](#))
- Any protocol deviation that results in a significant risk to the patient's safety

Patients who discontinue INC280 treatment should NOT be considered withdrawn from the study. They should return for the assessments indicated in [Section 7.2.1](#). If they fail to return for these assessments for unknown reasons, every effort (e.g. telephone, email, letter) should be made to contact them as specified in [Section 7.1.7](#).

The investigator must also contact the IRT to register the patient's discontinuation from study treatment.

Patients who become pregnant must cease all tumor assessments regardless of whether or not they developed Progressive Disease according to BIRC.

Patients who discontinue INC280 should be scheduled for an EOT visit as soon as possible and within 7 days of the last dose of INC280, at which time all of the assessments listed for the EOT visit will be performed. If a patient is discontinued from treatment at a study visit, the assessments performed at that visit will be considered as EOT assessments and do not need to be repeated. An End of Treatment Phase Disposition eCRF page should be completed, giving the date and reason for stopping treatment.

Patients who discontinue study treatment should enter either the survival follow-up period or continue tumor assessments, when appropriate.

Patients who have RECIST-defined Progressive Disease as determined by investigator and confirmed by the BIRC, but who, in the judgment of the investigator have evidence of continued clinical benefit from INC280 and the patient wishes to continue on the study treatment may continue to receive the study drug. These patients will continue assessments as detailed in [Table 7-1](#). In such cases, patients must complete the EOT visit only after permanent discontinuation of INC280. An End of Treatment Phase Disposition eCRF page should be completed, specifying the date of the subject's last treatment and reason for stopping study treatment.

## 7.1.5 Follow-up-period

### 7.1.5.1 Follow-up for Safety Evaluations

All patients must have safety evaluations for 30 days after the last dose of study treatment.

At the end of this period, the investigator should assess and discuss with the patient any AE observed/concomitant medication taken since discontinuation of study treatment. This can be done via a phone contact.

Data collected should be added to the Adverse Events eCRF and the Concomitant Medications eCRF. Antineoplastic therapies will be captured on the 'Antineoplastic therapies since discontinuation of study treatment' eCRF page.

Patients whose treatment is permanently discontinued due to an AE (clinical or based on abnormal laboratory value) must be followed until resolution or stabilization of the event, whichever comes first. In case of an abnormal laboratory value, blood tests should be repeated until resolution or stabilization.

### 7.1.5.2 Post-Treatment follow-up

All patients who discontinued treatment during the treatment phase for reasons other than death, lost to follow-up, pregnancy or disease progression as determined by investigator and confirmed by BIRC ([Section 7.1.4](#)) should not be considered withdrawn from the study and should continue with tumor [REDACTED] assessments every 6 weeks from EOT as per [Table 7-1](#) until disease progression is confirmed per BIRC, withdrawal of consent from tumor assessments, lost to follow-up, death or study terminated by Sponsor. Once the patient ceases tumor follow-up [REDACTED], the End of Post Treatment Disposition (Study Phase Completion) eCRF page should be completed. Antineoplastic therapies since discontinuation of study treatment will continue to be collected. If patients refuse to return for these visits or are unable to do so, every effort should be made to contact them or a knowledgeable informant by telephone to determine the survival status of the patient.

[figure not shown]

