Efficacy assessment of tumor response and progression will be performed every 6 weeks (i.e., every 2 cycles) from the first day of treatment with INC280 until RECIST 1.1 disease progression as determined by investigator and confirmed by Blinded Independent Review Committee (BIRC). This schedule must be followed regardless of dose interruptions.

Confirmation of response is required for all response endpoints, as per RECIST 1.1. All radiological assessments obtained at screening/baseline, during treatment and during the follow-up phase should be performed using the same modality (method) and will be submitted to the designated independent imaging vendor for review by BIRC.

Approximately 30 enrolled patients at selected sites (regardless of cohort assignment) will have full PK samples and ECGs collected. The rest of the patients will have sparse PK samples and ECGs collected (see [Table 7-6](#) and [Table 7-7](#)). At the time of eligibility confirmation, the IRT system will inform the site about which PK and ECG schedule should be followed by the patient.

[figure not shown]
In Cohort 1 and Cohort 5, all of the efficacy analyses will be performed separately for each of the two sub-cohorts.

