#### **4.1.4 Follow-up**

Regardless of the reason for discontinuation from study treatment, patients will be contacted for a safety follow-up 30 days after the last dose of INC280. At this time, the investigator will record any AEs/SAEs that may have occurred after discontinuation of study treatment and/or follow on resolution of ongoing AEs.

All patients who discontinue treatment with INC280 for any reason other than disease progression according to RECIST 1.1 as determined by investigator and confirmed by BIRC, death, withdrawal of consent for further assessments or lost to follow-up will continue to have tumor assessments as per their current schedule until disease progression is confirmed by BIRC, death, withdrawal of consent for further assessments, or lost to follow-up.

When the patient completes all follow-up assessments as required per protocol, a Study Evaluation Completion eCRF must be completed.

Information on new anticancer therapies initiated since discontinuation of study treatment will be collected.

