## 7 Visit schedule and assessments

### 7.1 Study flow and visit schedule

Table 7-1 lists all the assessments and indicates with an “X”, the visits when they are performed. All data obtained from these assessments must be supported in the patient’s source documentation. The table indicates which assessments produce data to be entered into the database (D) or remain in the source documents only (S) (“Category” column). The eCRF will not be used as a source document.

Written informed consent must be obtained before any study specific assessments are performed, including those at molecular screening and screening. Main screening evaluations and baseline radiological tumor assessments should be performed within 28 days of treatment start.

Each treatment cycle is 21 days (the 21 days cycle length is fixed regardless of whether the dose of INC280 is withheld).

All visits are to be scheduled according to the appropriate number of calendar days from Cycle 1 Day 1 of study drug administration. Every effort must be made to follow the schedule of assessments within the windows outlined in the protocol.

After screening:

- All assessments have a  $\pm 3$  day window unless otherwise indicated
- Radiological tumor assessments may be performed within a  $\pm 4$  day window, unless otherwise indicated
- If a given visit is out of window, the next visit should be performed with reference to the day of first dose in order to get the patient back on schedule
- If an off-schedule imaging assessment is performed, subsequent imaging assessments should be performed in accordance with the original imaging schedule
- Laboratory assessments and height/weight performed as part of the screening evaluations and within 7 days of the first dose of study drug, will not be required to be repeated on Cycle 1, Day 1
- All assessments on Cycle 1, Day 1 must be done prior to the first dose unless otherwise specified. It is recommended that the investigator checks the pre-dose laboratory results prior to starting treatment
- Patients who discontinue INC280 treatment must have EOT visit performed  $\leq 7$  days after stopping study drug
- Permitted contact windows for survival follow-up:  $+\text{-} 7$  days

Additional assessments may be performed as clinically indicated.

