Urinalysis (dipstick) with micro-analysis	D			X	If clinically indicated							
Serum pregnancy test (if applicable)	D			X	X	X	X	X	X			
Tumor assessments RECIST 1.1												
CT scan or MRI of chest, abdomen, pelvis ( EOT scan not required if previous scan was performed within ≤28	D	7.2.1		X				X	C5D1 and every 6 wks	X	X(every 6wks)	

Category	Protocol Section reference	Molecular pre-screening and Main Screening Phases	Study Treatment Phase							Post-treatment Follow-Up phase (safety follow-up within 30d of last dose for all patients and efficacy follow-up every 6 weeks until BIRC-confirmed disease progression)	Survival Follow-up Phase	
			Cycle 1 (21 days)		Subsequent cycles (21 days per cycle)			End of study treatment (EOT)				
Visit Name		Molecular pre-screen	Screening Visit (D-28 to D-1)	C1 D1	C1 D15	C2 D1	C3 D1	C4D1 C5D1 etc...	EOT Visit (within 7d of last dose)	Tumor Follow-Up (every 6 wks)	Study Evaluation Completion	Survival Follow-Up (every 3 mo)
days)												
Whole body bone scan	D		X						Only if clinically indicated			
CT scan or MRI of brain	D		X						C3D1 and every 6 wks (if positive at baseline) or if clinically indicated			
CT scan or MRI of other metastatic sites (e.g., neck, etc)	D		X (if other metastatic sites)						C3D1 and every 6 wks (if positive at baseline) or if clinically indicated			
Localized bone CT scan, MRI or X-ray (for any lesions identified on the whole body bone scan that are not visible on the chest/abdomen/pelvis CT scan or MRI)	D		X (only if lesions on whole body scan that are not visible on the CAP scans)						C3D1 and every 6 wks (if positive at baseline) or if clinically indicated			
Photography (for skin lesions)	D		X (only if skin lesions)						C3D1 and every 6 wks (if positive at baseline) or if clinically indicated			
Safety assessments												
Adverse events	D	8.1	Continuous until $\geq$ 30 days after the last dose of INC280									

Category	Protocol Section reference	Molecular pre-screening and Main Screening Phases	Study Treatment Phase						Post-treatment Follow-Up phase (safety follow-up within 30d of last dose for all patients and efficacy follow-up every 6 weeks until BIRC-confirmed disease progression)	Survival Follow-up Phase	
			Cycle 1 (21 days)		Subsequent cycles (21 days per cycle)			End of study treatment (EOT)			

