#### **7.2.1.2 Subsequent imaging for response assessment**

Imaging assessments as described in [Table 7-2](#) should be performed at the timepoints specified using the same imaging modality used at baseline, irrespective of study treatment interruption or actual dosing (see [Table 7-1](#)). Imaging assessments for response evaluation will be performed every 6 weeks starting from Day 1 of cycle 1 (+/- 4 days window).

Additional imaging assessments may be performed at any time during the study at the investigator's discretion to support the efficacy evaluations for a patient, if necessary. Clinical suspicion of disease progression at any time requires a physical examination and imaging assessments to be performed promptly rather than waiting for the next scheduled imaging assessment.

Each lesion that is measured at baseline must be measured by the same method (either same imaging method or by photography, including a metric ruler) and when possible, the same local radiologist/physician throughout the study so that the comparison is consistent. If an off-schedule imaging assessment is performed because progression is suspected, subsequent imaging assessments should be performed in accordance with the original imaging schedule.

Combined PET/CT may be used only if the CT is of similar diagnostic quality as a CT performed without PET, including the utilization of oral and IV contrast media. At the discretion of the Investigators, FDG-PET scans may be performed to document PD per RECIST 1.1 ([Appendix 1](#)).

All study imaging (including any off-schedule imaging studies) performed to evaluate progression or response should be submitted to the designated imaging vendor for quality control and review by the BIRC, promptly after acquisition.

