2.8 Analysis of secondary variables

2.8.1 Efficacy

All secondary endpoint analyses will be performed based on the FAS, unless otherwise specified. Efficacy will also be presented combining the MET mutant cohorts per line of treatment as defined in [Section 2.2](#).

No adjustment for multiple testing will be made.

Key secondary efficacy endpoints

The key secondary objective is to evaluate duration of response (DOR) as assessed by BIRC, by cohort.

Among patients with a confirmed response (PR or CR), DOR is defined as the time from first documented response (PR or CR) to the date of first documented PD or death due to any cause. If a patient has not had an event, DOR is censored at the date of last adequate tumor assessment.

The censoring and event date options to be considered for the main analysis are presented in [Table 2-1](#).

Table 2-1 Outcome and event dates for DOR and PFS analyses

Situation	Date	Outcome
A No baseline assessment	Date of first dose of study drug ^a	Censored
B Progression at or before next scheduled Assessment	Date of progression	Progressed
C1 Progression or death after exactly one missing assessment	Date of progression (or death)	Progressed
C2 Progression or death after two or more missing assessments	Date of last adequate assessment	Censored
D No progression	Date of last adequate assessment	Censored
E Treatment discontinuation due to 'Disease progression' without documented progression, i.e. clinical progression based on investigator claim	N/A	Information ignored. Outcome derived based on radiology data only.
F New anticancer therapy given	Ignore the new anticancer therapy and follow situations above	As per above situations
G Deaths due to reason other than deterioration of 'Study indication'	Date of death	Progressed

^a The rare exception to this is if the patient dies no later than the time of the second scheduled assessment as defined in the protocol in which case this is a PFS event at the date of death

DOR will be described in tabular and graphical format using Kaplan-Meier methods. The Kaplan-Meier estimate of the distribution function will be constructed. Kaplan-Meier curves

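### Protocol 7.1.5.2 times post-treatment scans from EOT, other sections from Cycle 1 Day 1; on an EOT clock the SAP's distance rule can censor a true PFS or DOR event after one missed scan

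*Protocol*

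**What the plan says.** Protocol 7.1.5.2, which covers patients who stop treatment without BIRC-confirmed progression, asks for tumor "assessments every 6 weeks from EOT as per" Table 7-1. The follow-up column of that table gives a six-week frequency but no starting point.

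Four other sections keep the original schedule:

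- Section 4.1.4, on the same patients: they "will continue to have tumor assessments as per their current schedule until disease progression is confirmed by BIRC".
- Section 7.2.1.2: "Imaging assessments for response evaluation will be performed every 6 weeks starting from Day 1 of cycle 1", with a window of 4 days either side.
- Section 4.1: six-weekly assessment runs "from the first day of treatment with INC280 until RECIST 1.1 disease progression as determined by investigator" and confirmed by BIRC.
- Section 7.1: "All visits are to be scheduled according to the appropriate number of calendar days from Cycle 1 Day 1 of study drug administration". Imaging done off schedule does not move the later dates.

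Two further rules decide whether there is a scan at EOT. Table 7-1 states "EOT scan not required if previous scan was performed within" 28 days. Section 7.1.4 adds: "If a patient is discontinued from treatment at a study visit, the assessments performed at that visit will be considered as EOT assessments".

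SAP 4.6.1 infers missing assessments from the distance between the last adequate assessment and the event. More than D1 (8 weeks) means one missing; more than D2 (14 weeks) means two. An assessment that was done but read as UNK also counts as missing. In SAP Table 2-1, row C1 ("Progression or death after exactly one missing assessment") keeps the event. Row C2 (two or more missing) censors it at the last adequate assessment. The table applies to both DOR and PFS.

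**The concern.** A site that follows the section devoted to post-treatment follow-up can restart the six-week clock at EOT. Because the EOT scan may be waived, the interval spanning EOT can then be well over six weeks with no scan missed. The SAP rule cannot tell a long scheduled gap from a missed scan.

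The longer gap alone does no harm, since an event after one assumed miss is kept. The harm comes when one follow-up scan is also not done or is UNK. The distance can then pass D2, two misses are assumed, and a real progression or death is removed. Dropping true events tends to lengthen estimated DOR, the key secondary endpoint, and PFS.

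**Working it through.** **Inputs.** Scan interval 42 days and window ±4 days (Protocol 7.2.1.2). EOT scan waived if the last scan was no more than 28 days earlier (Table 7-1). SAP 4.6.1 takes a two-week window. Let u be the days from the last adequate scan to EOT; with no EOT scan, u runs from 0 to 28.

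**The SAP's thresholds, reproduced.**

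- D1 = 42 + 14 = 56 days (8 weeks).
- D2 = 2 × 42 + 14 = 98 days (14 weeks).

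**Cycle 1 Day 1 schedule.**

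- No miss: 42 days, at most 42 + 8 = 50 with the windows at both ends. This is below D1.
- One miss: 84 days, at most 84 + 8 = 92. This is below D2, so row C1 applies and the event counts.

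**EOT clock, no EOT scan.** With no miss the distance to the next scan is 42 + u. With one miss it is 84 + u.

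| u (days) | No miss: 42 + u | One miss: 84 + u | Over D2 = 98? |
|---|---|---|---|
| 0 | 42 | 84 | no |
| 14 | 56 | 98 | no |
| 15 | 57 | 99 | yes |
| 21 | 63 | 105 | yes |
| 28 | 70 | 112 | yes |

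Solving 84 + u > 98 gives u > 14, so at nominal dates u = 15 to 28 is exposed. A scan 4 days late raises the maxima to 74 days (no miss) and 116 days (one miss), and exposure then starts at u = 11 (84 + 11 + 4 = 99).

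**An ordinary case.** A patient stops at the cycle visit midway between two scans, and that visit serves as EOT. Here u = 21, so no EOT scan is required. With one missed or UNK scan and progression on the next, the distance is 105 days and the event is censored. On the Cycle 1 Day 1 schedule one miss gives 84 days and the event counts.

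**If u exceeds 28,** an EOT scan is required. The distance restarts at EOT, one miss gives 84 days, and the event is kept.

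**Share exposed (assumptions, not in the documents).** If EOT falls evenly over the 42 days between scans, u is 15–28 in 14/42 = 33% of such patients. With a 5–20% chance that the next scan is missed or UNK, the share is 33% × 5% = 1.7% to 33% × 20% = 6.7%. This is an upper bound, because an event must also end that interval.

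**The case against.** The best counter-argument is that the schedule is already settled. Four sections keep the Cycle 1 Day 1 anchor, and Section 4.1.4 covers exactly these patients. The words in 7.1.5.2 may only mark when follow-up begins, and the sentence contains a redaction. On that reading the u = 21 patient missed two scans, due on days 42 and 84 after the last one, and the SAP is right to censor.

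That milder reading is possible, but 7.1.5.2 does not say it, and the table it cites gives no anchor. The redaction does not change the fact that the phrase governs tumor assessments. Counting two misses requires setting 7.1.5.2 aside; a site following that section missed one.

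It is also fair to say that the chain of conditions is long, that no frequency is documented, and that primary analyses have already been reported for every cohort (SAP 2.1). All of this stands and limits the point's weight. Rewording cannot change scans already taken. However, SAP 2.1 still plans updated efficacy analyses of the MET-mutant cohorts at last patient last visit, so a check of the data remains useful.

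Finally, SAP 4.6.1 uses a window of ±1 week where the protocol has ±4 days, and it mixes strict and non-strict inequalities for D2. Both are real inconsistencies. Neither changes the count on the Cycle 1 Day 1 schedule with D2 as stated, because 92 days is below 98 either way.

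**Conclusion.** The concern holds: 7.1.5.2 is wrong as written. It permits scan timing that contradicts four other sections and that the SAP's censoring rule mishandles. With on-time scans, an event after one real miss is censored when the last scan was 15–28 days before EOT and no EOT scan was done.

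The point is minor. It touches only DOR and PFS, only patients who stop without BIRC-confirmed progression, and only the interval spanning EOT. ORR is unaffected, since best response uses scans within 30 days of the last dose and no distance rule. The 1.7–6.7% rests on an assumed even spread of EOT dates and an assumed 5–20% miss rate. It applies only to patients at sites that used an EOT clock, and the number of such sites is unknown.

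**What to change.** In Protocol 7.1.5.2, delete the two words that anchor scans to EOT and add a clause keeping post-treatment scans on the six-week schedule from Cycle 1 Day 1. The D1/D2 thresholds then count missed scans correctly and need no change for this purpose.

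Where scans were already timed from EOT, count missed scans in the interval spanning EOT against that patient's actual due dates instead of by distance. The cost is one edited sentence and a check of one interval per affected patient.
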